4.2 Treatment period

A patient is defined as being on-study if they are continuing to have any study data collected, if the patient is receiving study specific treatment, is being followed for efficacy after discontinuation of protocol specific treatment, or is in follow-up (see [Table 2](#), [Table 3](#), and [Table 4](#)).

4.3 Follow-up period

Patients discontinuing study treatment should be scheduled for an End of Treatment (EOT) visit as soon as possible after their last dose. At that visit all assessments listed in the EOT visit column in [Table 2](#), [Table 3](#), and [Table 4](#) will be performed. If treatment is discontinued during a study visit, the EOT visit does not need to be repeated. The reason for stopping treatment and the date must be recorded in the eCRF.

4.3.1 30-day safety evaluation

After discontinuation from study treatment, patients must be followed for AEs for 30 days, after their last dose (see [Section 6](#)) or until new cancer therapy is started, whichever is shorter. This can be done via telephone contact at the Investigator's discretion. All concomitant medications received up to 30 days after the last dose of study medication should be recorded in the medical record and eCRF.

All new AEs occurring during this period must be reported and followed until resolution, unless, in the opinion of the Investigator, these values are not likely to improve because of the underlying disease. In this case, the Investigator must record his or her reasoning for this decision in the patient's medical records and as a comment in the eCRF.

All patients who have Grade 3 or 4 laboratory abnormalities (per NCI CTCAE v4.03 [<http://ctep.cancer.gov>]) at the time of discontinuation must be followed until the laboratory values have returned to Grade 1 or 2, unless in the opinion of the investigator it is not likely that these values are to improve. In this case, the investigator must record his or her reasoning for making this decision in the patient's medical records and as a comment on the eCRF.

4.3.2 Follow-up period

4.3.2.1 Follow-up for patients who discontinue treatment prior to disease progression

Patients discontinuing from AZD1775 in the absence of PD should have progression-free survival (PFS) CT assessments performed according to [Table 2](#), [Table 3](#), and [Table 4](#) until PD has been assessed by the Investigator. If PD has been assessed, patients will then be followed for survival.

4.3.2.2 Follow-up for patients who discontinue treatment due to disease progression

Patients with documented disease progression will be followed every 3 months for survival status (e.g., date and cause of death). Patients may be contacted during outpatient visits or by telephone. Information pertaining to the type and dates of administered post-treatment therapy will be collected when available (see [Table 2](#), [Table 3](#), and [Table 4](#)).

4.3.2.3 Final Protocol Visit and Beyond

The Final Protocol Visit (FPV) requirement applies only to patients who continue AZD1775 after the implementation of the Clinical Study Protocol (CSP) Version 5. Patients should return to the clinic soon after the CSP Version 5 is implemented in order to be re-consented on the associated updated ICF.

Beyond the FPV, patients may continue to receive AZD1775 if they are deriving clinical benefit, in the opinion of the Investigator, and not fulfilling any of the discontinuation criteria. Such patients are to be treated in accordance with local practice and as deemed appropriate by the Investigator to ensure continued safety monitoring of the patient while receiving the investigational product. It is recommended to continue observing ongoing patients at the frequency indicated within the study plans as described in [Table 3](#) and [Table 4](#). Restrictions regarding concomitant medications (refer to Section [7.8.2](#)) will be followed while the patient is receiving AZD1775. A change in AZD1775 dose/schedule should only occur for safety reasons, based on the Investigator's judgement, and should generally follow the approach for dose reduction and discontinuation as described in this protocol. Combining AZD1775 with other anti-cancer therapy is not allowed.

If a patient is no longer receiving benefit from AZD1775 beyond the FPV in the opinion of the treating physician, then the study drug should be stopped. The Investigator will inform AstraZeneca when a patient discontinues the study drug. Patients must return unused medication during routine clinic visits, and drug accountability information must continue to be collected in patient source documents until the patient discontinues treatment. In addition, provided that a patient gives proper informed consent, a plasma isolation (ctDNA) blood sample for future biomedical research should be obtained at the time of AZD1775 discontinuation, if due to disease progression. Patients will continue to be monitored for all SAEs, pregnancies, and overdoses for 30 days after the last dose of the investigational product.

5. STUDY ASSESSMENTS

The Sarah Cannon Development Innovations, LLC (Sarah Cannon) Trial Master electronic data capture (EDC) system will be used for data collection and query handling. The investigator will ensure that data are promptly and accurately recorded on the eCRFs as specified in the study protocol and in accordance with the instructions provided.

The Investigator ensures the accuracy, completeness, and timeliness of the data recorded and of the provision of answers to data queries according to the Clinical Study Agreement (CSA). The Investigator will sign the completed eCRFs. A copy of the completed eCRFs will be archived at the study site.

5.1 Efficacy assessments

5.1.1 Tumour assessments

RECIST v1.1 criteria will be used to assess patient response to treatment. The RECIST v1.1 guidelines for measurable, non-measurable, target lesions (TL) and non-target lesions (NTL) and the objective tumour response criteria (Complete Response [CR], Partial Response [PR], Stable Disease [SD] or progressive disease [PD]) are presented in [Appendix E](#).

The same method of assessment of tumour burden used at baseline (CT scans or magnetic resonance imaging [MRI] of the chest and abdomen/pelvis) must be used at each subsequent follow-up assessment (see [Table 2](#), [Table 3](#), and [Table 4](#)). Tumour imaging studies will be repeated every 8 weeks (± 1 week) relative to date of first dose for patients on the QD 5/9 treatment schema and every 9 weeks (± 1 week) relative to date of first dose for patients on the QD 5/2 treatment schema to assess response until objective disease progression as defined by RECIST v1.1 or withdrawal from study.

Categorisation of objective tumour response assessment will be based on the RECIST v1.1 criteria of response: CR, PR, SD and PD. Target lesion progression will be calculated in comparison to when the tumour burden was at a minimum (i.e. smallest sum of longest diameters previously recorded on study). In the absence of progression, tumour response (CR, PR, or SD) will be calculated in comparison to the baseline tumour measurements obtained before starting treatment.

If the Investigator is in doubt as to whether progression has occurred, particularly with regard to NTLs or the appearance of a new lesion, it is advisable to continue treatment until the next scheduled assessment or sooner if clinically indicated, and reassess the patient's status. If repeat scans confirm progression, then the date of the initial scan should be declared as the date of progression.

To achieve 'unequivocal progression' on the basis of non-target disease, there must be an overall level of substantial worsening in non-target disease such that, even in presence of SD or PR in target disease, the overall tumour burden has increased sufficiently to merit discontinuation of therapy. A modest 'increase' in the size of one or more NTL is usually not sufficient to qualify for unequivocal progression status.

It is important to follow the assessment schedule as closely as possible.

5.2 Safety assessments

A physical examination, medical history (to capture previous treatment medications and response to each prior treatment regimen), concomitant medications recorded ≤ 7 days prior to starting treatment, ECOG PS, complete blood count (CBC) with differential and platelets, clinical chemistry, and triplicate 12-lead ECG should be done at screening and prior to dosing on Day 1 of each cycle. Assessments at other time points are indicated in the study plan.

Vital signs (resting heart rate, blood pressure, temperature) and weight will be recorded at screening and at times shown in the study plan.

The following are additional AZD1775 project related assessments that should be carried out in addition to any standard protocol monitoring such as routine haematology/biochemistry, vital signs, and physical examinations.

5.2.1 Laboratory safety assessments

Blood samples for standard monitoring and determination of haematology and clinical chemistry safety will be taken at the times indicated in the Study Plan (see [Table 2](#), [Table 3](#), and [Table 4](#)).

Additional safety samples may be collected as clinically indicated and at the discretion of the Investigator. The date and results (values and units) will be recorded on the appropriate eCRF.

The clinical chemistry and haematology will be performed at a local laboratory. Sample tubes and sample sizes may vary depending on laboratory method used and routine practice at the study centre.

The following laboratory variables will be measured as a minimum (some of these variables may be measured at baseline only):

Laboratory Safety Variables

Haematology (2.7 mL whole blood sample)	Clinical chemistry (2.7 mL serum or plasma sample)	Coagulation (1.8 mL sample)	Pregnancy test
B-Haemoglobin	S/P-Albumin	B-PT or INR with PTT	Blood or urine
B-Leukocyte	S/P-Alanine transaminase (ALT)		
B-Haematocrit	S/P-Aspartate transaminase (AST)		

B-Red blood cell count	S/P-Alkaline phosphatase (ALP)
B-Absolute leukocyte differential count	S/P-Bilirubin, total
Neutrophils	S/P-Calcium, total
Lymphocytes	S/P-Creatinine
Monocytes	S/P-Chloride
Basophils	S/P-Potassium
Eosinophils	S/P-Sodium
B-Platelet count	S/P-Urea nitrogen or blood urea nitrogen

Pre-menopausal women of childbearing potential must have a negative urine or serum pregnancy test within 3 days prior to starting study treatment on Day 1, and a confirmatory test will be performed before treatment at the start of each cycle and at the EOT visit. In the event of suspected pregnancy during the study, the test should be repeated and, if positive, the patient discontinued from study treatment immediately.

The Investigator should make an assessment of the available results with regard to clinically relevant abnormalities. Any clinically significant abnormal laboratory values should be repeated as clinically indicated and recorded on the eCRF. The laboratory results should be signed and dated and retained at centre as source data for laboratory variables. For information on how AEs based on laboratory tests should be recorded and reported, see Section 6.3.6.

In case a patient shows an AST or ALT ≥ 3 x ULN and total bilirubin ≥ 2 x ULN please refer to [Appendix D](#) for further instructions.

5.2.2 Physical examination

A complete physical examination will be performed and will include an assessment of the following: general appearance; abdomen, skin, head and neck (including ears, eyes, nose and throat); lymph nodes and thyroid; and respiratory, cardiovascular, musculo-skeletal (including spine and extremities), and neurological systems.

If new or aggravated physical findings imply deterioration compared with baseline, the finding should be reported as an AE (Section 6). Performance status will be assessed using the ECOG performance status criteria (see Study Plan [Table 2](#), [Table 3](#), and [Table 4](#)).

5.2.3 Electrocardiogram

Triplicate 12-lead safety ECGs (paper ECG printout of 10 seconds for Investigator review) will be taken at screening and prior to dosing on Day 1 of each cycle (see [Table 2](#), [Table 3](#), and [Table 4](#)).

4, and Section 3.2). Triplicate ECGs should also be obtained to coincide with the non-food and food effect PK collections described in Table 2, Table 3 and Table 4. The triplicate ECG assessments must be performed before the PK sample is collected.

Triplicate ECG recordings should be taken within an approximate 5-minute period. QTc interval will be calculated using the Fridericia formula (per institutional standards) obtained from the 3 ECGs performed 2-5 minutes apart at study entry.

Additional ECGs may be taken at any other time the Investigator deems necessary for safety during the administration period. The patients will rest for at least 10 minutes before the start of each recording and they must be in the same supine body position (maximum 30 degrees flexion in the hip and feet not in contact with the footboard) at the recording time point.

The Investigator will judge the overall interpretation as normal or abnormal. If abnormal, it will be decided as to whether or not the abnormality is clinically significant or not clinically significant. The paper copy of each ECG reading will be retained with the patient's completed source documents. Only overall evaluation (normal/abnormal) will be recorded in the eCRF. If there is a clinically significant abnormal unscheduled ECG finding during the treatment period, this should be recorded on the AE eCRF, according to standard AE collection and reporting processes (see Section 6.3).

Attention should be paid to any detected increases in QTc interval. Patients who develop a single resting value of QTc interval of >450 msec/male and >470 msec/female or a shift from baseline of 60ms should stop taking AZD1775. Dosing can be resumed at a reduced dose (see section 6.7.3) after return of the resting QTc interval to pre-treatment status has been confirmed and correction of possible electrolyte imbalance has been made.

Monitoring of QTc, checking and correction of abnormal electrolyte levels and renal function are advised, especially in case of severe/prolonged diarrhoea. If QTc increases markedly from baseline, but stays below the above limits, a cardiologist's advice should be sought.

The concomitant use of ondansetron (known to prolong the QTc interval in rare cases, per labelling) should be taken into account when interpreting QTc changes.

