2.2 Secondary objectives

Secondary Objective :	Outcome Measure :
To evaluate the safety and tolerability of AZD1775 monotherapy in patients with locally advanced or metastatic solid tumours.	Treatment-emergent adverse events (TEAEs) and SAEs
To evaluate the preliminary anti-tumour activity of AZD1775 monotherapy in patients with locally advanced or metastatic solid tumours.	Best objective response (OR) to treatment will be assessed by dose level cohort according to Response Evaluation Criteria in Solid Tumours (RECIST) v1.1 (Eisenhauer et al 2009).
To evaluate the PK profile of AZD1775 monotherapy in patients with locally advanced or metastatic solid tumours.	PK parameters of AZD1775
To evaluate the preliminary effect of a high-fat meal on the PK profile of AZD1775 monotherapy in patients with locally advanced or metastatic solid tumours.	PK parameters of AZD1775
To characterise the effect of AZD1775 on QTc interval in patients with locally advanced or metastatic solid tumours.	QTc interval

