5.4 Pharmacokinetics

5.4.1 Collection of samples for AZD1775 PKs

Pharmacokinetic samples for AZD1775 (2 mL) will be collected throughout the study as indicated below. The date and actual time of the PK sample is to be recorded in the medical records and eCRF. Samples will be obtained at the time points indicated in [Table 5](#) and [Table 6](#).

Table 5 Pharmacokinetic sampling schedule for food effect patients

Time relative to first dose in cycle	Cycle 1 Day 1	Cycle 1 Day 5	Cycle 2 Day 1	Cycle 5 Day 5 and then every 3-5 cycles thereafter ^a	At response assessment (+/- 24 hrs)	At time of AEs possibly related to AZD1775	At end of treatment or progression (+/- 24 hrs)
Pre-dose	X ^b	X ^b	X ^b	X ^b			
1 hour	X ^b	X ^b	X ^b	-			
2 hours	X ^b	X ^b	X ^b	-			
4 hours	X ^b	X ^b	X ^b	-			
6 hours	X ^b	X ^b	X ^b	-			
8 hours	X ^b	X ^b	X ^b	-			
10 hours	X ^b	X ^b	X ^b	-			
Unscheduled					X	X ^c	X

^a Beyond the PK for Cycle 5 Day 5, collections will be flexible and may be obtained once every 3, 4 or 5 cycles (instead of 4 cycles) on day 3, 4 or 5 (instead of day 5).

^b Triplicate ECGs should be obtained to coincide with the food effect PK collections. The triplicate ECG assessments will be performed before the PK sample is collected.

^c Unless the last dose of study drug was administered > 1 week prior to the event (See Section 6.7).

^d PK samples will no longer be required after implementation of CSP Version 5.

Table 6 Pharmacokinetic sampling schedule for non-food effect patients

Time relative to first dose in cycle	Cycle 1 Day 1	Cycle 1 Day 5	Cycle 5 Day 5	Cycle 6 Day 3, 4, or 5 then every 3-5 cycles thereafter^a	At response assessment (+/- 24 hrs)	At time of AEs possibly related to AZD1775	At end of treatment or progression (+/- 24 hrs)
Pre-dose	X ^b	X ^b	X ^b	X ^b			
1 hour	X ^b	X ^b	-				
2 hours	X ^b	X ^b	-				
4 hours	X ^b	X ^b	-				
6 hours	X ^b	X ^b	-				
8 hours	X ^b	X ^b	-				
10 hours	X ^b	X ^b	-				
24 hours	X ^{b,c}	X ^{b,c}					
Unscheduled					X	X ^d	X

- ^a Beyond the PK for Cycle 5 Day 5, collections will be flexible and may be obtained once every 3, 4 or 5 cycles (instead of every 4 cycles) on day 3, 4 or 5 (instead of day 5).
- ^b Triplicate ECGs should be obtained to coincide with the non-food effect PK collections. The ECG assessments will be performed before the PK sample is collected.
- ^c 24 hour sample collected on Cycle 1 Day 2 and Cycle 1 Day 6 (only for QD schedule).

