8.4.3 Safety

Dose-limiting toxicities will be summarised by dose level cohort using the DLT analysis set. Additionally the following minimum data summaries will be presented by dose level cohort using the full analysis set:

- TEAEs of any CTCAE grade – summarised by MedDRA preferred term and system organ class and CTCAE maximum grade

- SAEs
- Deaths summarised by primary cause
- Laboratory parameters (hematology and chemistry), vital signs, ECG data and concomitant medications including evaluations for potential DILI

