9.4 Data management

Data management will be performed by Sarah Cannon according to the Data Management Plan (DMP). Data will be entered in the EDC system at the study site. Trained study personnel will be responsible for entering data on the observations, tests, and assessments specified in the protocol into the EDC system and according to the eCRF Instructions. The eCRF Instructions will also guide the study site in performing data entry. Data entered in the EDC system will be immediately saved to a central database and changes tracked to provide an audit trail.

The data will be validated as defined in the Data Management Plan. Quality control procedures will be applied to each stage of data handling to ensure that all data are reliable and have been processed correctly. The study DMP will describe in greater detail the methods used to collect, check, and process clinical data. It will also clarify the roles and responsibilities of the various functions and personnel involved in the data management process. The PI is responsible for signing the eCRF but this can be delegated to a trained Investigator. The eCRF is signed electronically as per the eCRF instructions.

Data Management determines the format of the data to be received from external vendors and coordinates the flow of data to an external environment or clinical database (if applicable). Data Management will ensure that the data collection tool (e.g., Interactive Web Response System [IWRS], etc.) will be tested and validated as needed. The data collected through third party sources will be obtained and reconciled against study data.

Adverse events and medical/surgical history will be classified according to the terminology of the latest version of the MedDRA. Medications will be classified according to the World Health Organisation (WHO) Drug Dictionary. All coding will be performed by AstraZeneca or delegate.

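### QTc interval is a secondary outcome, but section 5.2.3 puts only a normal/abnormal call for each ECG in the eCRF and no other route for numeric QTc is described

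*Protocol*

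**What the plan says.** Protocol section 2.2 (and the synopsis) lists this secondary objective: "To characterise the effect of AZD1775 on QTc interval in patients with locally advanced or metastatic solid tumours". Its outcome measure is the QTc interval.

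Collection is dense. Section 5.2.3 requires triplicate 12-lead ECGs at screening and before dosing on Day 1 of each cycle. In section 5.4.1, the footnotes to Tables 5 and 6 add the scheduled PK time points: "Triplicate ECGs should be obtained to coincide with the food effect PK collections" for food-effect patients and "Triplicate ECGs should be obtained to coincide with the non-food effect PK collections" for the others.

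Capture is narrow. After describing the investigator's overall interpretation, section 5.2.3 says of the tracings: "The paper copy of each ECG reading will be retained with the patient", meaning in the source documents at site. It then says: "Only overall evaluation (normal/abnormal) will be recorded in the eCRF". A clinically significant abnormal unscheduled finding goes on the AE form. On derivation, the same section has one sentence: "QTc interval will be calculated using the Fridericia formula (per institutional standards) obtained from the 3 ECGs performed 2-5 minutes apart at study entry".

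On analysis, section 8.4.3 lists among the minimum summaries by dose level cohort: "Laboratory parameters (hematology and chemistry), vital signs, ECG data and concomitant medications including evaluations for potential DILI". On data flow, section 9.4 says: "Data will be entered in the EDC system at the study site". It mentions external vendor data only in general terms and names no ECG vendor.

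**The concern.** The outcome is a quantity in milliseconds, and the only ECG variable that the protocol sends to the database has two levels. A QTc interval, or a change in it, cannot be derived from such a flag. The flag is not specific to QTc either: a patient with chronic rate-controlled atrial fibrillation, who may be eligible under exclusion criterion 16, could be called abnormal at every visit whatever the QTc. Conversely, a male patient whose QTc rises but stays below 450 ms could be called normal throughout.

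At stake is the answer to one secondary objective. Mean change from baseline, counts above the protocol's own limits and any relation between concentration and QTc would be unavailable from the database. The protocol lists QTc prolongation as an adverse drug reaction (section 1.2.3) and asks that ondansetron be taken into account when QTc changes are interpreted (section 5.2.3). Describing such changes by cohort needs the numbers.

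**Working it through.** No sample size, power or alpha figure is involved, and the protocol gives no figure to reproduce. The check follows QTc from objective to analysis and then counts the tracings.

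**Tracing the variable**

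| Step | Protocol | What exists |
|---|---|---|
| Objective | 2.2 | QTc interval, in ms |
| Measurement | 5.2.3, Tables 5 and 6 | Triplicate tracings on paper |
| Derivation | 5.2.3 | Fridericia, stated for study entry |
| Capture | 5.2.3 | Normal/abnormal only |
| Other route | 9.4 | Generic vendor transfer; no ECG reader named |
| Analysis | 8.3.4, 8.4.3 | ECG data summarised by cohort |

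The chain breaks at capture. Elsewhere the protocol asks for values: results with units for additional safety samples (5.2.1), tumour marker results (5.2.5), and the date and actual time of PK samples (5.4.1). The ECG, which is the only source for this outcome, carries an express restriction.

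**Tracings on the intensive PK days**

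Tracings = time points × days × 3.

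- Not in the food-effect assessment, once daily (Table 6): pre-dose, 1, 2, 4, 6, 8, 10 and 24 hours on Cycle 1 Days 1 and 5. That is 8 × 2 = 16 sets, and 16 × 3 = 48 tracings.
- Food-effect (Table 5): pre-dose, 1, 2, 4, 6, 8 and 10 hours on Cycle 1 Days 1 and 5 and Cycle 2 Day 1. That is 7 × 3 = 21 sets, and 21 × 3 = 63 tracings.

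Numeric QTc values entered from these under section 5.2.3 as written: 0.

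**Size of a back-entry exercise**

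Assume that all of the approximately 66 planned patients complete the intensive days.

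- By tracing: 66 × 48 = 3,168 if every patient followed Table 6, and 66 × 63 = 4,158 if every patient followed Table 5. The true mix lies between.
- By triplicate mean: 66 × 16 = 1,056 to 66 × 21 = 1,386 entries.

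Sets at screening, on Day 1 of later cycles and at later pre-dose PK samples are additional. Patients who did not complete the intensive days reduce the total.

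**The case against.** The strongest reply is that the disputed sentence directly follows the investigator's normal/abnormal judgement. It may only limit how much of that interpretation is entered, leaving measured intervals to be captured elsewhere. Section 8.3.4 says that ECG data will be collected for all patients, section 8.4.3 plans to summarise them, and section 9.4 refers to eCRF instructions and a data management plan that are not shown. This is possible, but none of these places names a route for QTc. If the eCRF does hold the fields, section 5.2.3 misdescribes it and still needs correcting.

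Several stronger readings are tempting, and the protocol does not support them.

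- A reader might infer that the QTc data are lost. They are not: every paper tracing is retained as source.
- A reader might infer that QTc safety decisions are compromised. The limits in milliseconds and the 60 ms shift (section 5.2.3 and Table 11) are applied at site from the printouts, and monitors have direct access to original records (section 9.2).
- A reader might infer that the database has no heart rate. Resting heart rate is a vital sign taken on Day 1 of each cycle (section 5.2.4). What is missing is heart rate or RR at each ECG.
- A reader might infer that no QTc excursion is captured. Clinically significant unscheduled findings reach the AE form. They are events, however, and not a QTc series.
- A reader might infer that QTcF is calculated only at study entry. Section 5.2.3 and Table 11 act on on-treatment QTc, so it must be determined then. The narrower point is that the formula is not stated for later time points.
- A reader might infer that ECGs accompany every PK sample. The ECG footnote in Tables 5 and 6 is on scheduled time points only.

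It also stands that the objective is descriptive, is one of five secondary objectives and does not drive the MTD, which rests on DLTs. Section 8.6 leaves PK-endpoint modelling to discretion.

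**Conclusion.** The contradiction holds in the current text. If the protocol is followed to the letter, the database cannot answer the QTc objective, and only counts of normal and abnormal could be tabulated by cohort. This is not a detail that can be left to a statistical analysis plan, which can define analyses only of values that are captured.

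The extent is limited. It is a gap between objective and data capture for one descriptive secondary outcome. It is recoverable from retained source, but no recovery is planned. The MTD/RP2D determination and on-site QTc management are untouched.

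The conclusion rests on the protocol alone and assumes that no eCRF field or ECG transfer exists beyond what it describes. Timing matters: Tables 2 to 4 show all schedules closed to enrolment, Version 5 moves patients to a final protocol visit, and section 9.4 restricts database changes after lock.

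**What to change.** Replace the capture sentence in section 5.2.3. For every scheduled triplicate set, record in the eCRF the date and time, heart rate or RR, QT and QTcF, in addition to the overall evaluation. Either each tracing or the triplicate mean will serve; the mean cuts entry to a third. Amend the derivation sentence so that the Fridericia correction is stated for all time points and not only for study entry. Back-enter the values from the retained printouts before database lock.

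Any baseline chosen should be labelled as serving the descriptive QTc summary only. Shift from baseline is also a trigger in section 5.2.3 and Table 11, and this change should leave those rules as they are.

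The cost is one eCRF page plus retrospective transcription and checking, roughly 3,200 to 4,200 tracings for the intensive days if all patients completed them, and fewer otherwise. No new ECGs are needed. If the sponsor judges that this is not worthwhile, the consistent alternative is to withdraw the QTc objective openly.
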